### 8.2.1. Physical Examinations

A physical examination, including height and body weight, will be carried out pre-vaccination during the screening period and, if deemed necessary by investigator, also on Day 1. At all other visits, an abbreviated, symptom-directed examination will be performed if deemed necessary by the investigator based on any clinically relevant issues, clinically relevant symptoms, and medical history. Symptom-directed physical examination may also be performed if deemed necessary by the investigator.

Physical examinations will be performed by the investigator or appropriately trained delegate. Any clinically relevant abnormalities or changes in severity noted during the review of body systems should be documented in the eCRF as an AE or SAE if it meets the criteria for an AE or SAE according to the protocol reporting requirements.

### 8.2.2. Vital Signs

Body temperature (oral route preferred), heart rate (beats per minute), respiratory rate (breaths per minute), and systolic and diastolic blood pressure (mm Hg) will be assessed.

Blood pressure and pulse/heart rate measurements will be assessed, if possible, with a completely automated device. Manual techniques will be used only if an automated device is not available.

Sitting systolic and diastolic blood pressure and heart and respiratory rate measurements should be preceded by at least 5 minutes of rest in a quiet setting without distractions (eg, television, cell phones). Vital signs evaluation is recommended before blood sampling.

Confirmatory vital signs measurement can be performed if inconsistent with a prior measurement. Any abnormalities or changes in severity noted during the review of vital signs should be documented in the eCRF.

Participants will utilize a diary to record body temperature measurements post-vaccination (see Section 8).

### **8.2.3. Clinical Safety Laboratory Assessments**

For participants in Cohorts 1 and 2, blood samples for serum chemistry and hematology will be collected at screening, on Day 1, and 7 days after vaccination (or at the exit visit if early exit is within 7 days after vaccination and the participant terminates from the study without withdrawing consent) as noted in [Appendix 2: Clinical Laboratory Tests](#). The investigator must review the laboratory results, document this review, and record any clinically relevant changes occurring during the study in the AE section of the eCRF. The laboratory reports must be filed with the source documents.

### **8.3. Adverse Events, Serious Adverse Events, Adverse Events of Special Interest and Other Safety Reporting**

Timely, accurate, and complete reporting and analysis of safety information, including AEs, SAEs, AESIs (including potential AESIs, refer to Section 8.3.6) and PQCs, from clinical studies are crucial for the protection of participants, investigators, and the sponsor, and are mandated by regulatory agencies worldwide. The sponsor has established Standard Operating Procedures in conformity with regulatory requirements worldwide to ensure appropriate reporting of safety information; all clinical studies conducted by the sponsor or its affiliates will be conducted in accordance with those procedures.

Adverse events will be reported by the participant (or, when appropriate, by a caregiver, surrogate, or the participant's legally acceptable representative) for the duration of the study.

Further details on AEs, SAEs, AESIs, and PQCs can be found in [Appendix 4](#).

#### **8.3.1. Time Period and Frequency for Collecting Adverse Event, Serious Adverse Event and Adverse Event of Special Interest Information**

##### **All Adverse Events**

AEs and special reporting situations, whether serious or non-serious, that are related to study procedures or that are related to non-investigational sponsor products will be reported from the time a signed and dated ICF is obtained until the end of the study/early withdrawal.

Clinically relevant medical events not meeting the above criteria and occurring between signing of ICF and moment of first vaccination will be collected on the Medical History eCRF page as pre-existing conditions.

Solicited AEs, collected through a participant diary, will be recorded for each vaccination from the time of vaccination until 7 days post-vaccination.

All other unsolicited AEs and special reporting situations, whether serious or non-serious, will be reported for each vaccination from the time of vaccination until 28 days post-vaccination. Unsolicited AEs with the onset date outside the timeframe defined above (>28 days after previous study vaccination), which are ongoing on the day of the subsequent vaccination, should be recorded as such.

All SAEs and AEs leading to discontinuation from the study (regardless of the causal relationship) and all AESIs are to be reported from the moment of vaccination until 6 months post vaccination. The sponsor will evaluate any safety information that is spontaneously reported by an investigator beyond the time frame specified in the protocol.

All COVID-19 cases will be collected for all participants for the duration of the study.

See Section 7.2 for procedures associated with withdrawal of consent.

All AEs will be followed until resolution or until clinically stable.

### **Serious Adverse Events**

All SAEs occurring during the study must be reported to the appropriate sponsor contact person by study site personnel immediately, but no later than within 24 hours of their knowledge of the event.

Information regarding SAEs will be transmitted to the sponsor using the Serious Adverse Event Form and Safety Report Form of the eCRF, which must be completed and reviewed by a physician from the study site, and transmitted to the sponsor immediately, but no later than within 24 hours. The initial and follow-up reports of an SAE should be transmitted electronically or by facsimile (fax). Telephone reporting should be the exception and the reporter should be asked to complete the appropriate form(s) first.

### **AESIs**

TTS is considered to be an AESI. Thrombotic events and/or thrombocytopenia (defined as platelet count below the lower limit of normal [LLN] range for the testing laboratory) are considered to be potential AESIs. All AESIs, including potential AESIs, will be reported to the sponsor from the moment of study vaccination until 6 months after the study vaccination (see Section 8.3.6).

### **8.3.2. Method of Detecting Adverse Events and Serious Adverse Events and Adverse Events of Special Interest**

Care will be taken not to introduce bias when detecting AEs, SAEs or AESIs. Open-ended and nonleading verbal questioning of the participant is the preferred method to inquire about AE occurrence.

---

**Solicited Adverse Events**

Solicited AEs are used to assess the reactogenicity of the study vaccine and are predefined local (at the injection site) and systemic events for which the participant is specifically questioned and which are noted by participants in their diary (see Section 8).

After vaccination, participants will remain under observation at the study site for at least 30 minutes for presence of any acute reactions and solicited events.

In addition, participants will record solicited signs and symptoms in a participant diary for 7 days post-vaccination. All participants will be provided with a participant diary and instructions on how to complete the participant diary (see Overview in Section 8). If a paper diary is used for this study, the study staff will transcribe the information provided by the participant into the relevant sections of the eCRF. If an e-diary is used, diary information will be transferred to the sponsor. After review and verbal discussion of the initial diary entries with the participant, the investigator will complete their own assessment in the relevant sections of the eCRF. Once a solicited sign or symptom from a participant diary is considered to be of severity Grade 1 or above, it will be recorded as a solicited AE.

***Solicited Local (Injection Site) AEs***

Participants will be asked to note in the participant diary occurrences of injection site pain/tenderness, erythema and swelling at the study vaccine injection site daily for 7 days post-vaccination (day of vaccination and the subsequent 7 days). The extent (largest diameter) of any erythema and swelling should be measured (using the ruler supplied) and recorded daily. The case definitions for solicited injection site events can be found in the references ([Gidudu 2012](#); [Kohl 2007](#)).

***Solicited Systemic AEs***

Participants will be instructed on how to record daily temperature using a thermometer provided for home use. Participants should record the temperature (oral route preferred) in the participant diary in the evening of the day of vaccination, and then daily for the next 7 days approximately at the same time each day. If more than 1 measurement is made on any given day, the highest temperature of that day will be used in the eCRF.

Fever is defined as endogenous elevation of body temperature  $\geq 38.0^{\circ}\text{C}$  ( $\geq 100.4^{\circ}\text{F}$ ), as recorded in at least 1 measurement ([Marcy 2004](#)).

Participants will also be instructed on how to note signs and symptoms in the participant diary on a daily basis for 7 days post-vaccination (day of vaccination and the subsequent 7 days), for the following events: fatigue, headache, nausea, and myalgia.

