##### Risks Related to Ad26/protein preF RSV Vaccine

The Ad26/protein preF RSV vaccine is currently being studied in 4 ongoing studies in more than 6,500 participants aged 60 years and older, including participants with comorbidities, to assess safety and immunogenicity and to investigate whether the vaccine prevents RSV disease. In these studies, the most commonly reported solicited local adverse events (AEs) were injection site

---

a Probable TTS is defined as a thrombotic/thromboembolic event reported in combination with a low platelet count [thrombocytopenia]

pain/tenderness and swelling (mild to moderate). The most frequently reported solicited systemic AEs were fatigue, muscle pain, headache, chills, joint pain, and nausea, which were mild to moderate in severity. These solicited AEs were short-lived and resolved within a few days. Overall, available results from these studies show the vaccine to be well-tolerated with no safety concerns.

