### **General Risks Related to Vaccination**

In general, IM injection may cause local itching, warmth, pain, tenderness, erythema/redness, induration, swelling, arm discomfort, or bruising of the skin. Participants may exhibit general signs and symptoms associated with IM injection of a vaccine, including fever, chills, rash, myalgia, nausea/vomiting, headache, dizziness, arthralgia, general itching, and fatigue. These side effects will be monitored, but are generally short-term and do not require treatment.

Syncope can occur in association with administration of injectable vaccines. Syncope can be accompanied by falls. Procedures should be in place to avoid falling injury. If syncope develops, participants should be observed until the symptoms resolve. Fear of injection might lead to fainting and fast breathing.

Participants may have an allergic reaction to the vaccination. An allergic reaction may cause a rash, urticaria, or even anaphylaxis. Severe reactions are rare. Participants with a known or suspected allergy, or with a history of anaphylaxis or other serious adverse reactions to vaccines or vaccine excipients (specifically the excipients of the study vaccine), will be excluded from the study.

After vaccination, participants will remain at the study site for at least 30 minutes and will be closely observed by study staff. Necessary emergency equipment and medications must be available in the clinic to treat severe allergic reactions.

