| 
 
To assess the safety and reactogenicity of various combinations of RSV vaccine components
 
                                                   | 
 
SAEs and AESIs from first dose administration until 6 months after vaccination
 
Solicited local and systemic AEs for 7 days after vaccine administration
 
Unsolicited AEs from the time of vaccine administration through the following 28 days
 
                                                                                                                                                                                                                                                                                                                                                                                                                                      |
| 
 
To assess humoral immune responses elicited by various combinations of RSV vaccine components
 
                                               | 
 
RSV neutralization antibody titers
 
                                                                                                                                                                                                                                                                                                                                                                                                                                                                                                                                                                                                                                                                   |

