**4.3. Justification for Dose**

Ad26.RSV-A.preF at dose levels of  $5 \times 10^{10}$  vp and  $1 \times 10^{11}$  vp (Phase 1/2a study VAC18193RSV1004), and at dose levels of  $1 \times 10^{11}$  vp,  $1.3 \times 10^{11}$  vp, and  $1.6 \times 10^{11}$  vp (Phase 2a study VAC18193RSV2005), combined with RSV-A preF protein showed an acceptable safety and reactogenicity profile in a population aged 60 years and older. Ad26.RSV-A.preF administered

alone at dose levels of  $5 \times 10^{10}$  vp and  $1 \times 10^{11}$  vp and RSV-A preF protein administered alone at a dose level of 150 µg has also been evaluated in study VAC18193RSV1004 and did not reveal any safety concerns. The Ad26/protein preF RSV vaccine containing a combination of  $1 \times 10^{11}$  vp Ad26.RSV-A.preF and 150 µg RSV-A preF protein has been evaluated in the Phase 2b study VAC18193RSV2001 and showed efficacy in preventing RSV-mediated LRTD.

Based on encouraging nonclinical immunogenicity and efficacy data, and available clinical data on the reactogenicity, immunogenicity, and efficacy of Ad26.RSV-A.preF and RSV-A preF protein, a range of vaccine formulations including Ad26.RSV-B.preF2 and RSV-B preF protein components was selected to be evaluated in the current study. As RSV preF protein at a dose level of 300 µg and Ad26 up to a dose level of  $2 \times 10^{11}$  vp will be evaluated for the first time in the current study, the safety and reactogenicity profile will be monitored closely. These dose levels have been evaluated in a nonclinical toxicity study and were shown to be well tolerated with no adverse vaccine-related findings observed.

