**Unsolicited Adverse Events**

Unsolicited AEs are all AEs for which the participant is not specifically questioned in the participant diary.

---

For details regarding AESIs, refer to Section [8.3.6](#).

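### The diary does not ask about chills or joint pain, two of the six systemic reactions the protocol reports as most frequent with the current vaccine, so their rates, severity and duration may be under-captured

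*Protocol*

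**What the plan says.** Protocol Section 8.3.2 has participants take a daily temperature, from which fever is derived, and record symptoms on the day of vaccination and the next 7 days "for the following events: fatigue, headache, nausea, and myalgia". The systemic table in Appendix 6 has rows for vomiting, nausea, diarrhea, headache, fatigue and myalgia. It has none for chills or joint pain.

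Section 2.3.1, drawing on four ongoing studies with more than 6,500 participants aged 60 or over, states: "The most frequently reported solicited systemic AEs were fatigue, muscle pain, headache, chills, joint pain, and nausea". Its paragraph on general vaccination risks repeats both symptoms in a list "including fever, chills, rash, myalgia, nausea/vomiting, headache, dizziness, arthralgia, general itching, and fatigue".

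On the role of these data, Section 8.3.2 says: "Solicited AEs are used to assess the reactogenicity of the study vaccine and are predefined local (at the injection site) and systemic events". In Section 3 the endpoint "Solicited local and systemic AEs for 7 days after vaccine administration" is primary for Cohorts 1 and 2, with equivalent wording for Cohort 3. Section 4.3, on 300 µg preF protein and Ad26 up to 2×10^11 vp, says that these "will be evaluated for the first time in the current study, the safety and reactogenicity profile will be monitored closely".

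Anything outside the diary has its own category: "Unsolicited AEs are all AEs for which the participant is not specifically questioned in the participant diary". That category is also primary in Cohorts 1 to 3: "Unsolicited AEs from the time of vaccine administration through the following 28 days".

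**The concern.** The sponsor names six systemic reactions as the most frequent with the product on which every new formulation builds, describes all six as solicited, and then prompts for only four of them (plus fever). The omission falls on the instrument that the protocol itself designates for measuring reactogenicity, in the part of the study whose safety and immunogenicity results decide the composition to take forward.

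At stake is how well the arms can be compared on two expected reactions. A prompted daily item gives an answer from nearly every participant on every day. A volunteered event gives an answer only from those who think to mention it.

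**Working it through.** No stated figure rests on this point, so the check is a comparison of texts, followed by an illustration on assumed rates.

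**1. The two lists**

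| Reaction named in Section 2.3.1 | In the diary list (8.3.2) | Row in Appendix 6, systemic |
|---|---|---|
| Fatigue | yes | yes |
| Muscle pain (myalgia) | yes | yes |
| Headache | yes | yes |
| Nausea | yes | yes |
| Chills | no | no |
| Joint pain | no | no |

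Not prompted: 2 of 6, or 33%. Nothing elsewhere in either document adds the two symptoms or explains their absence.

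**2. What happens to chills or joint pain under each route**

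| Feature | If solicited | As planned (unsolicited) |
|---|---|---|
| How elicited | daily diary prompt | open-ended questioning (8.3.2) |
| No report | a prompted non-report | counted as no event (SAP 5.3.2.4) |
| Grade 3 | fatigue and myalgia rows: incapacity with bed rest, or lost work or social activity, can qualify | general scale (10.4.3): inability to do usual activities and medical intervention |
| Tables | solicited, by class and derived term, with time to onset and duration (SAP 5.3.2.2) | separate, by SOC and PT |
| Causality | assessed by the investigator | assessed by the investigator |
| Dates | recorded | start and stop dates recorded (SAP 5.3.2.3) |
| Primary endpoint, Cohorts 1–3 | yes, 7 days | yes, 28 days |
| Pausing rule (6.9) | rule 6 | rule 4, same count, grade, relatedness and 72-hour terms |

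The routes differ in the first four rows only. On severity, a participant kept in bed by chills who needs no medical intervention fits the Grade 3 wording used for fatigue but not the general Grade 3 wording.

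**3. Where the comparison is made**

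In Table 6 of the protocol, Arms 2, 3, 4, 7 and 9 all carry 150 µg of each protein. Their total Ad26 doses are:

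- Arm 2: 0
- Arm 3: 2.5×10^10 + 2.5×10^10 = 5×10^10 vp
- Arm 4: 5×10^10 + 5×10^10 = 1×10^11 vp
- Arm 7: 1×10^11 + 5×10^10 = 1.5×10^11 vp
- Arm 9: 1×10^11 + 1×10^11 = 2×10^11 vp

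Each arm has 12 + 48 = 60 participants over Cohorts 1 and 2.

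**4. Illustration (true rates and capture fractions assumed, not from the documents)**

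Expected recorded cases per arm = 60 × true rate × capture fraction, with the same capture fraction in both arms.

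| Capture | True 10% vs 30%: cases | Difference | True 5% vs 20%: cases | Difference |
|---|---|---|---|---|
| 100% | 6 vs 18 | 20 points | 3 vs 12 | 15 points |
| 50% | 3 vs 9 | 10 points | 1.5 vs 6 | 7.5 points |
| 25% | 1.5 vs 4.5 | 5 points | 0.75 vs 3 | 3.75 points |
| 10% | 0.6 vs 1.8 | 2 points | 0.3 vs 1.2 | 1.5 points |

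Equal capture leaves the ratio between arms unchanged and shrinks the absolute difference and the counts.

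**5. Effect on the participant-level percentage**

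The percentage with any solicited systemic AE falls only by the share of participants who have chills or joint pain and none of fever, fatigue, headache, nausea or myalgia. The documents do not give that share, and it could be close to zero. The same argument applies to Grade 3 or higher.

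**The case against.** The best case against the point is that little is lost. Volunteered chills and joint pain remain inside a primary endpoint, tabulated both overall and for vaccination-related events. They carry dates from which duration can be derived, and they fall under a pausing rule with parallel terms. Sites telephone 2 to 4 days after vaccination and discuss diary entries with the participant, so there are openings to report. Participants and assessors are blinded, so capture should be similar across arms. The study is descriptive and sets no numerical reactogenicity threshold for selection. Section 2.2 reports an acceptable reactogenicity profile for Ad26 doses from 3.7×10^9 to 1.6×10^11 vp with 150 µg protein. Only Arm 9 goes above that range.

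Most of this stands, and it rules out several stronger readings that a reader might infer:

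- *Causality is handled worse for unsolicited events.* It is not. Only injection-site reactions are related by definition (10.4.2), and the SAP plans a table of related solicited systemic events.
- *The overall percentages with any, or with Grade 3, solicited systemic AEs are understated.* Step 5 shows that this cannot be established.
- *Dose differences are blunted.* The documents do not say that chills or joint pain rise with Ad26 dose, and step 4 rests on assumed rates.
- *The loss of comparability with earlier studies defeats an objective.* Comparing Arms 1b and 13 with those studies is not a planned analysis.

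The objection does not answer the mismatch itself. It also leaves the reliance on spontaneous report, the different Grade 3 wording and the separate tables.

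**Conclusion.** The point holds in a limited form. Two of the six reactions that the protocol reports as most frequent are neither prompted nor given a systemic grading row, without explanation. Their event-specific rates, severity and duration may be under-captured when formulations are compared. How much is lost cannot be derived: the documents give no rate for either symptom and no rate of spontaneous reporting.

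The conclusion assumes that open-ended questioning captures fewer events than a daily prompt. It also assumes that the reaction profile in Section 2.3.1, which describes the RSV-A product, is a fair guide to the new combinations; Section 2.3.1 says there are no clinical data for the RSV-B components. This is a worthwhile, inexpensive improvement and not a flaw that invalidates the safety assessment.

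**What to change.** Add chills and joint pain to the solicited systemic list in Section 8.3.2 and to the diary, and give each a row in Appendix 6 worded like fatigue and myalgia. SAP 5.3.2.2 would then tabulate them as it stands. These events would move from pausing rule 4 to rule 6, and the protocol should acknowledge that; no change to the rules is proposed here.

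For any cohort already enrolled, add a SAP table of unsolicited chills and arthralgia with onset within 7 days of each vaccination, placed beside the solicited table and labelled as unprompted. If the two symptoms are to stay unsolicited, state why and keep that side-by-side table for all cohorts.

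The cost is two more daily items over 8 diary days (2 × 8 = 16 entries per vaccination), two grading rows and two coded terms. If the items start only with Cohort 3, prompted data would be missing for the 60 participants from Cohorts 1 and 2 in the 210 that Section 9.2.3 counts for the selected formulation: 60/210 = 29%.
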